8.4 Reporting Procedures – Notifying the IRB

Any AE, SAE and UP will be recorded by the study PI and will be reported to IRB and other necessary sites immediately.

8.5 Study Halting Rules

The study will be halted when three grade 3 AEs determined to be “probably related” are reported and enrollment screens will stop accepting new study participants.

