5.9 Premature Termination or Suspension of Study

This study may be temporarily suspended or prematurely terminated if there is sufficient reasonable cause. Written notification, documenting the reason for study suspension or termination, will be provided by the suspending or terminating party to investigator and regulatory authorities. If the study is prematurely terminated or suspended, the PI will promptly inform the IRB and will provide the reason(s) for the termination or suspension.

Circumstances that may warrant termination or suspension include, but are not limited to:

- Data that are not sufficiently complete and/or evaluable
- Insufficient compliance to protocol requirements
- Determination of unexpected, significant, or unacceptable risk to participants
- Determination of futility
- Lack of funding

Study may resume once concerns about safety, protocol compliance and data quality are addressed and satisfy the sponsor, IRB and/or FDA.

CONFIDENTIAL

6 Study Agent and Procedural Intervention

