8.2 Classification of an Adverse Event

8.2.1 Severity of Event

For AEs not included in the protocol defined grading system, the following guidelines will be used to describe severity.

- **Mild** – Events require minimal or no treatment and do not interfere with the participant's daily activities.

CONFIDENTIAL

This material is the property of the NYU School of Medicine and Langone Medical Center. Do not disclose or use except as authorized in writing by the study sponsor

- **Moderate** – Events result in a low level of inconvenience or concern with the therapeutic measures. Moderate events may cause some interference with functioning.
- **Severe** – Events interrupt a participant’s usual daily activity and may require systemic drug therapy or other treatment. Severe events are usually potentially life-threatening or incapacitating.

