8.2.2 Relationship to Study Agent

For all collected AEs, the clinician who examines and evaluates the participant will determine the AE’s causality based on temporal relationship and his/her clinical judgment. The degree of certainty about causality will be graded using the categories below.

- **Definitely Related** – There is clear evidence to suggest a causal relationship, and other possible contributing factors can be ruled out. The clinical event, including an abnormal laboratory test result, occurs in a plausible time relationship to drug administration and cannot be explained by concurrent disease or other drugs or chemicals. The response to withdrawal of the drug (dechallenge) should be clinically plausible. The event must be pharmacologically or phenomenologically definitive, with use of a satisfactory rechallenge procedure if necessary.
- **Probably Related** – There is evidence to suggest a causal relationship, and the influence of other factors is unlikely. The clinical event, including an abnormal laboratory test result, occurs within a reasonable time after administration of the drug, is unlikely to be attributed to concurrent disease or other drugs or chemicals, and follows a clinically reasonable response on withdrawal (dechallenge). Rechallenge information is not required to fulfill this definition.
- **Possibly Related** – There is some evidence to suggest a causal relationship (e.g., the event occurred within a reasonable time after administration of the trial medication). However, other factors may have contributed to the event (e.g., the participant’s clinical condition, other concomitant events). Although an AE may rate only as “possibly related” soon after discovery, it can be flagged as requiring more information and later be upgraded to “probably related” or “definitely related,” as appropriate.
- **Unlikely to be related** – A clinical event, including an abnormal laboratory test result, whose temporal relationship to drug administration makes a causal relationship improbable (e.g., the event did not occur within a reasonable time after administration of the trial medication) and in which other drugs or chemicals or underlying disease provides plausible explanations (e.g., the participant’s clinical condition, other concomitant treatments).

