8.3 Time Period and Frequency for Event Assessment and Follow-Up

The occurrence of an AE or SAE may come to the attention of study personnel during study visit or during the remote follow up period. All AEs including local and systemic reactions not meeting the criteria for SAEs will be captured. Information to be collected includes event description, time of onset, clinician’s assessment of severity, relationship to study product (assessed only by those with the training and authority to make a diagnosis), and time of resolution/stabilization of the event. All AEs occurring while on study must be documented appropriately regardless of relationship. All AEs will be followed to adequate resolution.

Any medical condition that is present at the time that the participant is screened will be considered as baseline and not reported as an AE. However, if the study participant’s condition deteriorates at any time during the study, it will be recorded as an AE. UPs will be recorded in the data collection system throughout the study.

CONFIDENTIAL

This material is the property of the NYU School of Medicine and Langone Medical Center. Do not disclose or use except as authorized in writing by the study sponsor

Changes in the severity of an AE will be documented to allow an assessment of the duration of the event at each level of severity to be performed. AEs characterized as intermittent require documentation of onset and duration of each episode.

The PI will record all reportable events with start dates occurring any time after informed consent is obtained until the last day of study participation. At each study visit, the investigator will inquire about the occurrence of AE/SAEs since the last visit. Events will be followed for outcome information until resolution or stabilization.

All unresolved adverse events should be followed by the investigator until the events are resolved, unless the subject is lost to follow-up, or the adverse event is otherwise explained. At the last scheduled visit, the investigator should instruct each subject to report any subsequent event(s) that the subject, or the subject's personal physician, believes might reasonably be related to participation in this study.

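### The mandatory safety halt in section 8.5 names only probably related events, so read literally severe events judged definitely related do not count toward it

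*Combined protocol and SAP*

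**What the plan says.** Section 8.5 is a single mandatory sentence. It begins "The study will be halted when three grade 3 AEs determined to be", and the only causality level it then names is probably related. The consequence is that enrollment closes to new participants. Probably related stands in quotation marks in the protocol, which marks it as a defined category. The sentence has no qualifier such as 'at least' or 'or definitely'.

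That category comes from section 8.2.2, which has five levels: Definitely, Probably, Possibly, Unlikely and Not Related. The top level is described as follows: "There is clear evidence to suggest a causal relationship, and other possible contributing factors can be ruled out". The same section says of a possibly related event that "it can be flagged as requiring more information and later be upgraded to" either of the two higher levels.

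Section 8.2.1 defines severity as Mild, Moderate or Severe, without numbers. It opens: "For AEs not included in the protocol defined grading system, the following guidelines will be used to describe severity". No such grading system appears in the protocol text, and the attachments listed in section 18 were not available to me.

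Other provisions bear on safety:

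- Section 5.9 lists circumstances that may warrant suspension, among them "Determination of unexpected, significant, or unacceptable risk to participants".
- Section 8.4 states: "Any AE, SAE and UP will be recorded by the study PI and will be reported to IRB and other necessary sites immediately".
- Section 10.2.6 stops the trial for excess anesthetic failure and says that this is not a safety matter.
- Section 10.2.8 plans no safety analysis.

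**The concern.** A halting rule should respond at least as strongly when the evidence that the drug caused the harm is stronger. As written, 8.5 does not. An event first graded possibly related adds one to the count if it is raised to probably related. It adds nothing if it is raised straight to definitely related.

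This matters because 8.5 is the only quantitative safety trigger in the plan and the only mandatory one. Section 8.6 places oversight with the PI and co-investigators and describes no independent board. A fixed count is there so that stopping for harm does not rest on their discretion alone. The events it should catch are conceivable: section 2.4.1 describes convulsions and respiratory or cardiac arrest after small head-and-neck doses. A reaction soon after the block would have a clear link in time to the drug.

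**Working it through.** The plan gives no derivation or operating characteristics for the threshold of three, so there is no figure of its own to reproduce. The check is a reading of the text, followed by illustrations under stated assumptions.

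**Step 1: which events count.** Inputs are the threshold of 3 (8.5), the causality levels (8.2.2), and grade 3 read as Severe, the third of three levels in 8.2.1. That last reading is an inference. Take three Severe events, each judged probably (P) or definitely (D) related:

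| Mix | Literal count | Literal rule halts? | Count if P or D | Halts? |
|---|---|---|---|---|
| 3P, 0D | 3 | yes | 3 | yes |
| 2P, 1D | 2 | no | 3 | yes |
| 1P, 2D | 1 | no | 3 | yes |
| 0P, 3D | 0 | no | 3 | yes |

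The mixes are not equally likely. The table shows only which ones the literal rule misses.

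**Step 2: how often it would matter, given three such events.** Let q be the share of Severe, probably-or-definitely related events that are judged definite. The documents do not give q. It is an assumption, as is independent grading.

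- Chance that the literal rule fires at the third such event: (1 − q)³
- Expected number of such events when it fires: 3/(1 − q)

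| q | (1 − q)³ | 3/(1 − q) |
|---|---|---|
| 0.05 | 0.95³ = 0.857 | 3.2 |
| 0.10 | 0.90³ = 0.729 | 3.3 |
| 0.25 | 0.75³ = 0.422 | 4.0 |
| 0.50 | 0.50³ = 0.125 | 6.0 |

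If both categories count, the values are 1 and 3.

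**Step 3: how often it would matter overall.** Let r be the chance that a participant has a Severe, probably-or-definitely related event, with n = 100 enrolled (section 10.1, sample size). The documents give no value for r, so this too is an assumption. The chance of a halt during the trial is P(X ≥ 3), with X binomial(100, r) if both categories count and binomial(100, r(1 − q)) under the literal wording.

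| r | Both count | Literal, q = 0.05 | Literal, q = 0.10 | Literal, q = 0.25 | Literal, q = 0.50 |
|---|---|---|---|---|---|
| 2% | 0.323 | 0.296 | 0.269 | 0.190 | 0.079 |
| 5% | 0.882 | 0.859 | 0.833 | 0.728 | 0.458 |
| 10% | 0.998 | 0.997 | 0.995 | 0.983 | 0.882 |

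If every such event were judged definite, the literal rule would never fire at any r.

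**Step 4: which q is plausible.** Section 8.2.2 asks a definite event to have other factors ruled out and a plausible response to withdrawal. The drug is given at one sitting, so the low rows are the likelier ones.

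**The case against.** The strongest reply is that this is a slip with an obvious meaning. Section 8.2.2 introduces its categories as degrees of certainty, and a threshold on an ordered scale is naturally read as a minimum. An event with clear evidence and other causes ruled out also meets the description of a probable one. It is hard to picture an investigator who sees three severe, definitely related events and decides that 8.5 does not apply. An event reported as probable and later raised to definite has arguably been counted already, so step 1 overstates the problem for such events.

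The numbers also rest on inputs that the documents do not give. Section 2.4.1 calls adverse events rare in dental treatment, so three severe related events may never occur. At the low end of q the expected delay is small: 3.2 events instead of 3.

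Finally, there are other safeguards. Section 8.4 sends every AE to the IRB, section 10.1.2 breaks the blind for the individual after an AE and informs the PI, and section 8.6 provides direct faculty oversight.

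Most of this stands as a limit on consequence. It does not change the wording. The defined term in 8.5 is one of two separate categories, 8.2.2 treats them as alternative outcomes of an upgrade, and none of the safeguards requires a halt.

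**Conclusion.** The concern holds for the automatic rule read literally. Definitely related Severe events contribute nothing to the mandatory halt, and no other section makes up for that with a required stop.

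The practical size is modest. Even so, at an assumed q of 0.05 the literal rule misses the third such event about one time in seven (1 − 0.857 = 0.143), and at 0.10 about one time in four (1 − 0.729 = 0.271). These figures are conditional on three such events occurring, on independent grading and on grade 3 meaning Severe. The causality gap itself does not depend on that last reading.

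This should be fixed, because a mandatory safety threshold should give the intended answer without interpretation.

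**What to change.** Reword the trigger in section 8.5 to: three Severe (as defined in 8.2.1) AEs judged probably or definitely related. The count of three stays as the sponsor set it.

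If the grading system mentioned in 8.2.1 exists in an attachment, cite it in 8.5 in place of 8.2.1 and write 'grade 3 or higher', so that the same gap does not reappear on the severity side.

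The cost is one amended sentence, with IRB approval of the amendment as section 13.2 requires. No new data are needed, because section 8.3 already collects severity and relationship to study product for every AE.

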8.6 Safety Oversight

It is the responsibility of the PI and NYS Dental Licensed Co-investigators to oversee the safety of the study. NYS Dental Licensed Co-investigators who are full time faculty members of the department oversee every step of diagnosis, treatment planning and treatment on the PG endodontic clinic where this study will take place. PI and NYS Dental Licensed Co-investigators will be also overseeing the diagnosis, treatment planning, study interventional procedure and standard of care treatment process which is a part of the study by working closely with the treating PG students. This safety monitoring will include careful assessment and appropriate reporting of adverse events as noted above, as well as the construction and implementation of a site data and safety-monitoring plan. Appropriate reporting of AE as well as proper and ethical construction and implementation of the study sight and safety monitoring will be carried out by the PI. Proper data safety monitoring and oversight will be carried out by the Co-Investigator; [name].

9 Clinical Monitoring

Clinical site monitoring is conducted to ensure that the rights and well-being of human subjects are protected, that the reported trial data are accurate, complete, and verifiable, and that the conduct of the trial is in compliance with the currently approved protocol/amendment(s) by the PI on a regular basis, including all the steps in the study; data collection, data verification of endpoint, and safety.

9.1 Data Safety and Monitoring Plan

The sources of the documents are the preoperative questionnaires, immediate and follow-up postoperative questionnaire collected either on paper form or in REDCap. All source documents will be stored securely in REDCap. Paper forms or documents will be securely locked on 4th floor room 407 and will be only be accessible to study team. The PI will ensure safety of the subjects by regular data monitoring, giving the accurate access permissions in REDCap as well as to the securely locked drawer.

Access to study records will be limited to IRB-approved members of the study team. The investigator will permit study-related monitoring, audits, and inspections by the IRB, the government regulatory bodies, and University compliance and quality assurance groups of all study related documents (e.g. source documents, regulatory documents, data collection instruments, study data etc.).

CONFIDENTIAL

10 Statistical Methods

10.1 Sample Size Determination

Based on a previous study, the mean change of overall OHIP-14 scores from baseline at 1 month follow up is 6 with a standard deviation of 13.3 (27). Assuming the mean change from preoperative baseline at day 1 and day 5 postoperatively in the lidocaine group is 6 and the standard deviation is 13.3 and assuming the standard deviation of the change from baseline at day 1 and day 5 postoperatively is the same in the bupivacaine group, then with 40 subjects in each of the 2 groups there is 80% power to detect a difference in the change from preoperative baseline of +/-9.3 between the 2 groups. Assuming significance level of 2.5% using a 2-sided 2-sample t-test (assuming the data are Normally distributed). The testing is done at 2.5% because the null hypothesis will be rejected if at least one of the changes, either from baseline to day 1 postoperatively or from baseline to day 5 postoperatively, is significantly different between the 2 groups.

Considering the dropout rate after randomization will be 20%, the total number of subjects need to be enrolled is 100. The dropped-out subjects are those who are needed to be excluded because of intraoperative exclusion criteria, and who are not compliant to complete postoperative questionnaires. NYU Dentistry, endodontic clinic is a busy clinic. We will most of the time recruit subjects from the endodontic emergency care where on a daily basis, on average 5 patients are being treated. However, we are unsure of how many cases will be screened in order to reach this approximate sample size but we will update the protocol as this information is obtained.

10.2 Statistical Analysis

10.2.1 Analysis Dataset

The analysis dataset for study and control group will include subjects who receive IANB either with the study agent Bupivacaine or the control agent Lidocaine for the pulpectomy/endodontic debridement of symptomatic mandibular molar teeth diagnosed with either symptomatic irreversible pulpitis or pulp necrosis and periapical diagnosis of normal periapical tissues, asymptomatic or symptomatic apical periodontitis. The dataset will consist of preoperative data (demographics, preoperative pain assessment, PCS, LOT-R), initial clinical examination (cold test, percussion hypersensitivity), diagnosis, intraoperative data, initial and follow up OHIP-14 scores and postoperative pain, medication use and numbness. All analyses will be intent-to-treat dataset that includes all randomized patients and will use the analysis dataset.

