5.3 Intraoperative Exclusion criteria

An individual who meets any of the following criteria will be excluded from participation in this study:

1. Patients, whose endodontic treatment cannot be continued due to intra-procedural findings such as tooth fracture.
2. Any unexpected intraoperative procedural errors that might change the course of the treatment, such as separated instrument, perforation.
3. Patients whose adequate lip numbness is not obtained with 2 inferior alveolar nerve blocks.

CONFIDENTIAL

This material is the property of the NYU School of Medicine and Langone Medical Center. Do not disclose or use except as authorized in writing by the study sponsor

4. Patients whose adequate pulpal anesthesia is not obtained after 2 supplemental injections of anesthetic.

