5.5 Strategies for Recruitment and Retention

Patients recruited in this study will be mostly those who present for emergency dental treatment at NYU Dentistry Endodontic Clinic. The dental providers are postgraduate students from the endodontic department and they work under the supervision of the NYS Dental Licensed faculty, listed as Co-Investigators, who will be overseeing the procedures and treatments which are part of the study. Study investigators (the PI, Co-PIs;) will identify patients who need an emergency treatment either by inquiring directly to the dental providers at the start of the clinic session and through the day or by asking the front desk patient representatives in the Endodontic clinic if any emergency patients presented on that day. It is also possible that some patients who come for a treatment appointment might have a symptomatic tooth.

The potential participant's standard of care clinical and radiographic examination findings, diagnosis and treatment plan approved by the faculty will be prescreened by one of the study investigators after the standard of care clinical and radiographic examinations performed by the treating dentist to determine whether the patient is eligible in terms of diagnosis and treatment plan approved by the faculty by reviewing the gathered findings. This will be done in an effort to not to increase the wait time period for patients. After prescreening, potential participant will be asked by their dental provider if they are interested in discussing participation in a research study regarding postoperative pain with a research investigator. Interested subjects will be introduced to the study – this means the purpose of the study will be explained, details of what will be involved if they decide to participate will be described, duration of the study etc. by the PI or the Co-I; [name]. If they agree to participate, they will be consented by the PI or the Co-I; [name].

Interested potential subjects will be screened for eligibility by one of the study investigators and will be enrolled if they meet all the eligibility criteria.

We estimate 80 subjects (randomized to 40 participants per arm) are required. We estimate that loss of subjects will be minimal due to a short follow up time of 1 week, however in order to anticipate a greater loss of subjects because of intraoperative exclusion criteria, we will increase our sample size to 100 to include 20% attrition (n=50 per treatment group).

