5.8 Participant Withdrawal or Termination

5.8.1 Reasons for Withdrawal or Termination

Participants are free to withdraw from participation in the study at any time upon request. An investigator may terminate participation in the study if:

- Any clinical adverse event (AE), or other medical/dental condition or situation occurs such that continued participation in the study would not be in the best interest of the participant.
- The participant meets an exclusion criterion (either newly developed or not previously recognized) that precludes further study participation – this may include intra-operative factors outlined in the Intraoperative Exclusion Criteria including: fracture of the tooth, not having adequate lip numbness after 2nd inferior alveolar nerve block, or not having adequate pulpal anesthesia after two times supplemental injection.
- Failure of the subject to adhere to protocol requirements such as not completing the remote questionnaires after the treatment.

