7.1 Study Procedures/Evaluations

7.1.1 Study Specific Procedures

1. Screening, Consent and Preoperative Data Collection:

The potential participant's standard of care clinical and radiographic examination findings, diagnosis and treatment plan approved by the faculty who are NYS Dental Licensed Co-Investigators, will be prescreened by one of the study investigators after the standard of care clinical and radiographic examinations performed by the treating dentist to determine whether the patient is eligible in terms of diagnosis and treatment plan approved by the faculty by reviewing the gathered findings. This will be done in an effort to not to increase the wait time period for patients.

After prescreening, potential participant will be asked by their dental provider who are PG students who work under the supervision of Co-Investigators, if they are interested in discussing participation in a research study regarding postoperative pain with a research investigator. Interested subjects will be introduced to the study by the PI or Co-I; [name]. If they agree to participate, they will be consented by the PI or Co-I; [name].

Interested potential subjects will be screened for eligibility by one of the study investigators and will be enrolled if they meet all the eligibility criteria.

The following questionnaires will be completed to collect demographic information, psychological state information and trait characteristics, preoperative pain, and baseline oral quality of life information:

- Subject Demographic and Medical/Dental/Pain History Form
- Pain Catastrophizing Scale (PCS)
- Oral Health Impact Profile (OHIP14)

2. Randomization and Blinding:

Subjects will be assigned a de-identified subject number upon enrollment in the study. Subjects will be randomly assigned to one of two study groups in a 1:1 ratio just before receiving anesthesia; 0.5% Bupivacaine with 1:200,000 epinephrine OR 2% Lidocaine with 1:100,000 epinephrine.

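### Section 10.2.1 labels every analysis intent-to-treat on all randomised patients, but the intraoperative exclusions follow randomisation, are counted as dropout in the sample size, and have no stated OHIP-14 follow-up

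*Combined protocol and SAP*

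**What the plan says.** Section 10.2.1 gives two descriptions of the analysis set. The dataset "will include subjects who receive IANB either with the study agent Bupivacaine or the control agent Lidocaine", and then: "All analyses will be intent-to-treat dataset that includes all randomized patients and will use the analysis dataset".

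On timing, section 7.1.1 says "Subjects will be randomly assigned to one of two study groups in a 1:1 ratio just before receiving anesthesia"; the randomisation text in 10.1.1 agrees.

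Section 5.3 then excludes four kinds of patient during the procedure:

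- "Patients, whose endodontic treatment cannot be continued due to intra-procedural findings such as tooth fracture"
- "Any unexpected intraoperative procedural errors that might change the course of the treatment, such as separated instrument, perforation"
- "Patients whose adequate lip numbness is not obtained with 2 inferior alveolar nerve blocks"
- patients without adequate pulpal anaesthesia after two supplemental injections.

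Section 5.8.1 lets the investigator end participation when "The participant meets an exclusion criterion (either newly developed or not previously recognized) that precludes further study participation", and gives intraoperative factors as examples. Sections 5.8.2, 6.1.7 and 7.1.1 repeat that anaesthetic failures are removed from the study. The one later use that 5.8.2 states for them is a comparison of anaesthetic success.

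Section 5.5 expects little loss during follow-up but raises the sample size from 80 to 100 "in order to anticipate a greater loss of subjects because of intraoperative exclusion criteria". Section 10.1 (Sample Size Determination) assumes 20% dropout after randomisation. It defines the dropouts as intraoperative exclusions plus patients who do not complete the questionnaires. Section 10.2.3 tests the day 1 and day 5 changes separately and gives no rule for a missing OHIP-14.

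**The concern.** An intent-to-treat analysis needs an outcome, or a stated way of handling its absence, for every randomised patient. This plan promises that set, sizes the trial on a smaller one, and describes outcome collection in a way that appears to supply only the smaller one.

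The removed patients are not all removed for neutral reasons. Failure of lip numbness is a direct result of the randomised block. Pulpal failure is partly so, because the supplemental injections are lidocaine in both arms (2.2.2, 6.1.7). Fracture and procedural error need not be related to the drug, but they also break the promise to include all randomised patients. Section 2.1 describes bupivacaine's success as inferior by one measure and comparable by another, so unequal exclusion is possible and its direction cannot be presumed.

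If exclusion differs by arm, and excluded patients would have had a different OHIP-14 change, the comparison loses the protection of randomisation. Day 1 and day 5 scores that are not collected on time cannot be recovered.

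**Working it through.** **1. The plan's own figure.** Inputs from 10.1: 40 per arm, difference 9.3, SD 13.3, two-sided alpha 0.025, two-sample t-test.

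- SE = 13.3 × √(2/40) = 2.974; noncentrality = 9.3/2.974 = 3.127; critical t (78 df) = 2.285.
- Power = 79.8%, against the stated 80%. The detectable difference at 80% power is 9.32, against the stated 9.3.
- Enrolment: 80/(1 − 0.20) = 100.

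The figures reproduce. The stated power therefore belongs to the 80 patients left after exclusions and non-completion, not to the 100 randomised.

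**2. The sections side by side.**

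| Section | Population |
|---|---|
| 10.2.1, first sentence | received the study block |
| 10.2.1, last sentence | all randomised |
| 10.1 sample size | randomised, less intraoperative exclusions and non-completers |

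Patients still supplying OHIP-14 would not need to be counted as dropouts in a power calculation for OHIP-14. This is the strongest sign that no follow-up of excluded patients is intended.

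**3. Possible bias (illustration; all rates and correlations are assumptions).** The documents give neither an exclusion rate by arm nor a link between exclusion and OHIP-14. Assume 50 per arm, no true effect, and a standard normal difficulty score with correlation r to OHIP-14 change. The most difficult fraction q of each arm is excluded. The mean difficulty of those retained is E(q) = −φ(z)/(1 − q), where z is the (1 − q) normal quantile. The bias is [E(q₁) − E(q₂)] × r × 13.3.

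E(0.05) = −0.109, E(0.10) = −0.195, E(0.15) = −0.274, E(0.20) = −0.350.

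| Exclusion by arm | Bias in points, r = 0.2 to 0.7 | Simulated type I error per test (nominal 2.5%) |
|---|---|---|
| 10% v 10% | 0 | 2.5% |
| 10% v 5% | 0.2 to 0.8 | 2.6% to 3.2% |
| 15% v 10% | 0.2 to 0.7 | 2.6% to 3.1% |
| 20% v 10% | 0.4 to 1.4 | 2.7% to 4.6% |

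Example: (0.350 − 0.195) × 0.7 × 13.3 = 1.44 points. A harsher assumption is that excluded patients differ from retained ones by a full SD, with 30% v 10% excluded. That gives 0.20 × 1.0 × 13.3 = 2.66 points and about 8.7% per test. The error rates are per test; the plan rejects on either day, and no trial-level rate was computed.

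**4. Power if excluded patients are followed.** Same t-test and SD. Dilution means that a share of analysed patients shows no arm difference, so that 10% dilution gives 9.3 × 0.9 = 8.37 points. The 10% missing and the dilution shares are assumptions.

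| Analysed per arm | No dilution | 10% dilution | 20% dilution |
|---|---|---|---|
| 50 | 88.7% | 80.6% | 69.8% |
| 45 (10% missing) | 84.8% | 75.8% | 64.6% |

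**The case against.** **The absence of follow-up is inferred.** Section 7.1.1 sends surveys to subjects without expressly barring excluded ones. Figure 1, the schedule table and the survey forms are not visible. This stands as a limit on certainty: a reader might infer that the plan says follow-up stops at exclusion, and it does not say so in terms. The exclusion wording and the dropout definition in 10.1 nevertheless point that way, and if follow-up is intended, one sentence settles it.

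**It is not strictly a completers analysis.** A reader might call it that, but 10.2.3 tests each day separately, so a patient with only a day 1 score can enter the day 1 test. Available-case among patients not excluded is the accurate description.

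**The 20% is not all intraoperative exclusion.** Section 5.5 alone could suggest that it is. Section 10.1 names two sources and gives no split, so the share affected is unknown.

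**The exclusions may be deliberate.** The null hypothesis in 2.3 concerns patients exposed to each drug who go on to debridement. Sections 2.2.2 and 10.1.2 explain that repeated injections may themselves add pain. The dataset sentence in 10.2.1 could even be read as patients debrided under the study block. A question limited to patients with successful study anaesthesia is legitimate, but it is not intent-to-treat, and the plan would have to say so.

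**The illustrated bias is small.** This stands. The case for change rests on the contradiction and on unrecoverable data, not on those figures.

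**Conclusion.** The concern holds. The population declared in 10.2.1 and the one implied by 5.3, 5.8 and 10.1 cannot both be the primary population. Carried out as it reads, the plan would give an available-case comparison, selected partly on an effect of the randomised drug, under an intent-to-treat label.

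Confidence is high on the contradiction. It is lower on the absence of follow-up, which is an inference from the available text.

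The size of any bias is unknown. It is zero if similar patients are excluded equally from both arms, and about 0.2 to 1.4 points under the main illustrative assumptions, against 9.3. A reader might infer that the trial is biased for or against bupivacaine, or that a 9.3-point finding could be an artefact. The documents support neither: they give no exclusion rates by arm, and the background evidence on success is mixed. Even with no bias, the result would describe only patients whose procedure was completed under successful study anaesthesia.

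This should be fixed before enrolment, or at once if enrolment has begun.

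**What to change.** Leave clinical handling as it is and change what is collected and analysed.

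1. **Follow-up.** In 2.2.2, 5.3, 5.8.1, 5.8.2, 6.1.7, 7.1.1 and 10.1.2, state that a randomised patient who meets any of the four 5.3 criteria leaves the study anaesthetic protocol but stays in the existing remote surveys, including OHIP-14 on days 1 and 5. Amend the further-participation wording in 5.8.1 to match.
2. **Population.** In 10.2.1, replace both descriptions with one primary set: all randomised patients, analysed as randomised. Make the set without intraoperative exclusions a sensitivity analysis; this also addresses the worry about extra injections.
3. **Missing OHIP-14.** In 10.2.3, name one method that uses arm and baseline variables, for example multiple imputation from baseline OHIP-14 and preoperative pain. It should not rely on exclusion reason unless some excluded patients have observed scores, since otherwise nothing informs that term. Say how the method works with the Wilcoxon alternative.
4. **Sample size.** In 10.1, count only missing OHIP-14 as dropout and restate power.

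The cost is wording, a few more remote surveys of patients already consented, and possibly power. With 10% missing, 80% power for 9.3 points needs 41/0.9, or 46 enrolled per arm, without dilution; 50/0.9, or 56, with 10% dilution; and 63/0.9 = 70 with 20%. The planned 50 per arm is enough only if dilution is slight: at 45 analysed, 5% dilution leaves 80.6%. The question also becomes the effect of assigning the anaesthetic.

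If excluded patients cannot be followed, drop the intent-to-treat label and name the set a modified population. Report exclusions by arm and reason, and limit the conclusion to patients treated under successful study anaesthesia. That costs only wording, but gives up the intent-to-treat claim.
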